4.1 Inclusion and exclusion criteria for young children with cancer

4.1.1 Inclusion Criteria

- (1) Aged 6~14 years old;
- (2) Diagnosed with cancer;
- (3) Undergoing cancer treatment;
- (4) Able to communicate in Chinese;

4.1.2 Exclusion criteria

Children with physical impairment, cognitive impairment, or impaired mental status are excluded.

4.2 Inclusion and exclusion criteria for parents of children with cancer

4.2.1 Inclusion Criteria

- (1) Able to communicate in Chinese and read Chinese;
- (2) Able to use smartphone with WeChat;

4.2.2 Exclusion criteria

Parents with emotional or psychiatric disorders and cognitive problems are excluded.

4.3 Removal criteria

- (1) Tumor recurrence, bone marrow transplantation, or death during the intervention;
- (2) Transfer to a hospital for maintenance treatment;
- (3) The child and their families request to withdraw.

Compliance with any of the above conditions can be removed.

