5.4 Statistical analysis

5.4.1 Sample size

The number of sample cases required for the study was estimated by two sample content calculation using physical activity as the outcome measure. Taking the medium and high intensity physical activity of the study subjects as the observed outcome indicator, according to the results, the mean and standard deviation of physical activity minutes of the control group was 35.88 ± 50.39 , the mean and standard deviation of the experimental group was 166.19 ± 116.92 , and the test level was set at 0.05 and the control was 90%. Calculate the formula according to the sample size:

$$n = \frac{(Z_\alpha + Z_\beta)^2 * 2\sigma^2}{\delta^2}$$

We calculated 20.8621 subjects in the experimental group and the control group, considering 20% lost to follow-up, so $n_1=n_2=21/0.8=26.2527$ cases. At least 27 subjects were needed in the experimental and control groups.

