5.4.2 Statistical Analysis

The Epidata3.1 database was established, the data was entered by two people, and the SPSS25.0 statistical software was used for statistical analysis, and the test level was set at $\alpha = 0.05$.

(1) Description statistics: ① Data following normal distribution are described by mean and standard deviation; ② data without normal distribution are described by median and interquartile spacing.

(2) Data analysis: (3) Use Excel to establish the database, double input data, and use SPSS25.0 statistical software for statistical analysis, as follows:

① Using frequency, composition ratio, mean, standard deviation to describe the general data of children with tumors and their parents, the disease data of children and other conditions;

② The t-test, chi-square test or rank sum test were balanced for general data, physical activity, physical activity self-efficacy, physical activity enjoyment, and physical activity social support between the experimental and control groups.

③ One-way repeated measures analysis of variance was used to compare the number of high intensity physical activity minutes between children and parents in the experimental group.

④ If the data of physical activity, physical activity self-efficacy, physical activity enjoyment and physical activity social support meet the normal distribution (Shapiro-Wilk test) and equal variance (scatter plot), the mixed design analysis of variance shall be used to intervene the effects of main effect, time main effect, intervention time effect and confounding factors; if not satisfied, the generalized

estimation equation is used.

6. Research intervention

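### In standard form the planned ANOVAs drop every child with a missed visit, and neither section 4.3 nor section 5.4.2 names an analysis set that would prevent it; the likely cost is modest and the remedy is cheap

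*Combined protocol and SAP*

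**What the plan says.** Section 4.3 lists three grounds for removal: "Tumor recurrence, bone marrow transplantation, or death during the intervention"; "Transfer to a hospital for maintenance treatment"; and withdrawal at the family's request. It closes with "Compliance with any of the above conditions can be removed". It does not say whether removal is from the intervention, the follow-up or the dataset.

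Section 5.4.1 sizes the trial "considering 20% lost to follow-up" but does not say how those children are analysed.

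Section 5.4.2 names two ANOVAs. Item ③ reads "One-way repeated measures analysis of variance was used to compare" and applies to activity minutes in the experimental group, with no condition attached. Under item ④, "the mixed design analysis of variance shall be used" for outcomes that pass the normality and equal-variance checks; otherwise GEE is used. No analysis set and no rule for missed visits is given. The nearest text is section 5.3(4), which promises a remedial plan for incomplete questionnaires without content and does not mention removed children.

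Section 7 schedules activity at T0 to T4, self-efficacy and enjoyment at T0 to T3, and family support at T0, T3 and T4.

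**The concern.** A conventional repeated-measures or mixed-design ANOVA needs a complete row for each child. A child who completes T0, T1 and T2 and is then removed contributes nothing, although three questionnaires are on file. The plan expects one child in five to be lost, so this is a foreseeable event, and no wording in 4.3 or 5.4.2 stops it.

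Two analysts following the text could analyse different children: all enrolled, or only those with every visit. The set could also differ by outcome, because the visit schedules differ, and it could turn on a Shapiro-Wilk result, because GEE can keep partial records and the ANOVA does not. At stake are some precision and, if loss is related to activity and acts differently in the two groups, some bias of unknown sign. The groups are enrolled one after the other and removal is worded as discretionary, so equal loss in the two groups cannot be taken for granted.

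**Working it through.** **Inputs from the documents.** 27 per group, 20% loss, control 35.88 (SD 50.39), experimental 166.19 (SD 116.92), all from 5.4.1; visit schedule from section 7. **Assumptions not in the documents:** loss is permanent and spread evenly over the four intervals between visits; equal correlation of 0.5 between visits unless stated.

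**1. The plan's own loss step.** 21/0.8 = 26.25, rounded up to 27. This reproduces. The uninflated 20.8621 does not follow from the stated means and SDs, but that is a separate matter and nothing here depends on it.

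**2. What is left out.** 27 × 0.20 = 5.4 children lost per group; 27 − 5.4 = 21.6 complete. For activity, a lost child has on average (1+2+3+4)/4 = 2.5 questionnaires, so 5.4 × 2.5 = 13.5 are on file from incomplete children. The total collected is 21.6 × 5 + 13.5 = 121.5, and 13.5/121.5 = 11.1% would go unused.

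**3. Precision of change T0 to T3, five-visit outcome, random loss.** With outcome variance σ², the variance of one child's change is 2(1 − 0.5)σ² = σ². Completers: σ²/21.6 = 0.0463σ² per group. For a likelihood mixed model, sum the inverse covariance matrices of the visits each child has (80% with five visits, 5% each with four, three, two and one), invert the sum and take the T3 − T0 contrast: 0.0415σ². The reduction is 1 − 0.0415/0.0463, about 10%. Outcomes with fewer scheduled visits gain less: for those measured T0 to T3, a child lost after T3 is still complete.

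**4. Bias.** One simulated case: no treatment effect, gamma outcome at the control figures, 20% lost by T4 in one group with the hazard doubled below the median of the last observed value, random loss in the other group, correlation 0.3/0.5/0.7. Bias in minutes:

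| Analysis | Group difference at T3 | Change from T0 at T3 | Change from T0 at T4 |
|---|---|---|---|
| Completers | 1.20/1.57/1.90 | 0.01/−0.03/−0.01 | −0.44/−0.28/−0.19 |
| Unweighted GEE, all visits | 0.60/0.97/1.30 | 0.60/0.97/1.30 | 0.75/1.31/1.71 |
| Likelihood mixed model | 0.16/0.15/0.12 | 0.16/0.15/0.12 | 0.14/0.20/0.12 |

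For GEE and the mixed model I take the bias in change to equal the bias at the visit, because every child has T0. In a second case, with normal data and loss driven by earlier change, completers' change was biased by 0.02 to 0.04 SD and the mixed model was near zero.

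**5. Against the trial's precision.** At the control SD, the standard error of a group difference with 21.6 per group is 50.39 × √(2/21.6) = 15.3 minutes. A bias of 1.2 to 1.9 minutes is 8% to 12% of that.

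**6. When equal selectivity is not enough.** If the least active 20% are lost in both groups at the planned values, the control mean rises by 7.64 (lognormal) or 8.77 (gamma) and the experimental mean by 27.00 or 30.86. The net bias is 27.00 − 7.64 = 19.4 or 30.86 − 8.77 = 22.1 minutes. This is an extreme illustration. It shows that equal selectivity gives zero bias only when both groups share one distribution.

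**7. Which route applies.** The SD ratio is 116.92/50.39 = 2.32. For gamma or lognormal data at the control figures, Shapiro-Wilk rejects in 98% to 100% of samples of 27. Under item ④, activity minutes would therefore most likely go to GEE. Item ③ has no such check and stays an ANOVA.

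**The case against.** The strongest reply is that this is a gap in wording with little consequence. Much of that stands. For activity minutes the between-group comparison will most likely be by GEE, which can keep partial records, so the mixed-design ANOVA matters mainly for the secondary scales. Item ③ concerns the experimental group alone and so is not a between-group comparison of completers. The group-by-time term, which carries the treatment effect, was almost unbiased for completers in the first simulated case. Power is not threatened: on the plan's own inputs it is 99.7% at 21 per group with the root-mean-square SD and 95.1% with the larger SD.

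GEE on all visits is also not a cure. Unweighted, it generally needs loss to be completely at random, and in the first case it was more biased than completers for change from T0.

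What does not fall is that the plan names methods that discard incomplete children while expecting 20% loss, and gives no rule that would keep them.

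A reader might infer that removed children's data are deleted, or that a completers-only comparison is prescribed. The documents support neither: 4.3 is permissive and names no object, and 5.4.2 is silent.

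**Conclusion.** The point holds in a limited form. Both ANOVAs in 5.4.2, run in the standard way, would leave out about 5.4 of 27 children per group on a five-visit outcome, and nothing in 4.3 or 5.4.2 prevents it. The expected gain from correcting this is about 10% lower variance for change at T3, given correlation 0.5 and evenly spread random loss, together with protection when loss depends on observed values.

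A reader might go further and conclude that the treatment effect will be materially biased. The documents do not support that: they give no information on how loss relates to activity, and the simulated biases are small beside a standard error of about 15 minutes. Bias is zero if loss is unrelated to activity, or if it is equally selective in both groups and both have the same outcome distribution. Otherwise its sign is unknown. Confounding by enrolment period is a separate question that this point does not address.

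**What to change.** **Section 5.4.2.** Replace both ANOVAs with a likelihood-based mixed model (group, visit, group-by-visit) on all enrolled children with T0 data, in the group in which they were enrolled, using every questionnaire collected. The within-group change sought in item ③ is a contrast from the same model. Handle outcomes after death explicitly, so that no values are implied beyond death. Keep completers as a sensitivity analysis. If the GEE fallback is used, keep partial records but do not present this as removing bias.

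**Section 4.3.** State that removal does not take data already collected out of the analysis unless the family withdraws consent to its use. The clinical discontinuation rule stays with the sponsor. Report removals by group and reason.

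**Cost.** Wording in two sections and slightly more analysis work, with no new visits or data. The model assumes missing at random, which the data cannot verify, and a child with only T0 data adds little. Weighting GEE for loss is not proposed, because about five lost children per group are too few for stable weights.

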4.4 Recruitment and retention strategies

- (1) Children were recruited during hospitalization, and children diagnosed with

malignant tumors between 6 to 14 years in pediatric 1 and their parents were selected as the research objects, and baseline data of children and their parents were collected by questionnaire survey;

- (2) Ask the children about their subjective feelings, opinions and suggestions on their physical activity intervention, and timely improve the intervention forms, intervention programs and intervention measures to meet the needs of the children and their parents and improve the retention rate and compliance;
- (3) In the offline group parent-child activities and knowledge competitions, reward families, children and parents with outstanding performance and obvious progress, including stationery, dolls, toys, candy, etc.

5. Research Design

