The Effects of Parent-Child Activity Program on Physical Activity of Children With Cancer

March 31, 2024

1. Summary

Study Population: Children diagnosed with malignant tumors aged 6 to 14 years.

Outcome measures: ① Main outcome measures: physical activity behavior in children with cancer; ② secondary outcome indicators: height, weight, BMI, body fat, muscle, self-efficacy of physical activity, physical activity enjoyment, perceived social support in physical activity, and physical activity of parents.

Study Intervention: ① Control group: the children and their parents receive routine care and health education guidance, receive physical activity guidelines and suggestions for patients with malignant tumors provided by the researchers, and issue health knowledge education manual. In addition, the researchers and other members of the intervention team do not provide information about parent-child activities; ② Experimental group: the experimental group receives online and offline family-based parent-child physical activity intervention. It includes participating in offline group parent-child activities during hospitalization, including family competitive games and knowledge contests, etc., popularizing science of physical activity and parent-child sports activities to children and parents regularly after discharge, and pushing tweets, sports and practice videos related to physical activities and parent-child sports activities. Exercise were followed every 4 weeks and assessed for the previous session. The intervention protocol lasts 12 weeks and is followed up 3 months after the intervention is completed.

Sample size: with physical activity as the outcome indicator, the sample content was used to estimate the sample content calculation method, and the test level α was set to

0.05, and the control degree was 90%. According to the results of the literature review, 20.8621 subjects in the experimental group and the control group, considering 20% lost to follow up, so at least 27 subjects in the experimental group and the control group.

2. Introduction

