6.1 Study Intervention

(1) Implement routine care in the control group

Children in the control group and their parents received routine care and health education guidance, as well as guidelines and suggestions on physical activity of patients with malignant tumors provided by the investigator, and issued health knowledge education manuals. In addition, the investigator and other members of the intervention team did not provide information on parent-child activities;

(Ii) The experimental group received the family-based parent-child physical activity intervention combining online and offline, specifically as follows:

(1) Information support:

I . Establish and use wechat groups

After obtaining the informed consent, the children with cancer and their parents were invited to join the wechat group, and the popular science of physical activity related knowledge was regularly pushed to the children and their parents every week. Children and their parents have any questions can be asked to the intervention team members in the group. In addition, every Monday, the researchers sent the physical activity clock in the group, inviting the children and parents to record after completing the physical activity.

II . Create and use a wechat official account

Create a wechat official account, and push tweets and video content related to physical

activity every Thursday, Saturday and Sunday morning.

III . Offline group parent-child activities

Inform the children with cancer and their parents to follow up every 4 weeks, and organize the follow-up children and their parents to participate in offline group parent-child activities.

(2) Personnel support:

I . Promote parental participation

- ① Improve parents 'physical activity knowledge, belief and ability: through wechat group, wechat public account and other ways, increase parents' understanding of children's physical activity knowledge, improve their belief and ability to supervise and participate in children's physical activity.
- ② Increase parent-child activities to promote parents' participation: push a variety of parent-child physical activities, such as two-person aerobics, two-person ball sports, and outdoor sports requiring family participation (such as mountain climbing), etc.
- ③ Organize family competitive games to promote parent-child interest.
- ④ Enhance parent-child communication, and jointly develop solutions to various problems.

II . Strengthen the role between families —— peer influence

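### The retention measures in section 4.4 reach only the experimental group, which risks unequal, motivation-related loss and may also encourage over-reporting of activity in that group

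*Combined protocol and SAP*

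**What the plan says.** Section 4.4 of the combined protocol and SAP covers recruitment and retention. Item (1) deals with recruitment and baseline data. Item (2) is to "Ask the children about their subjective feelings, opinions and suggestions on their physical activity intervention" and to adapt the programme accordingly, so as to "improve the retention rate and compliance". Item (3) is to "reward families, children and parents with outstanding performance and obvious progress, including stationery, dolls, toys, candy, etc". How progress is judged is not stated.

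Both measures belong to the experimental group. Section 1 says of that group's programme: "It includes participating in offline group parent-child activities during hospitalization, including family competitive games and knowledge contests". Section 6.1, under the experimental group, uses the four-weekly follow-up to "organize the follow-up children and their parents to participate in offline group parent-child activities". Controls receive routine care, activity guidelines and a manual, and "the investigator and other members of the intervention team did not provide information on parent-child activities".

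Sections 5.2 and 7 set data collection at T0 to T4 without distinguishing the groups. Section 3.2.1 makes the CLASS-C questionnaire the measure of the children's physical activity. Section 7 has it completed on paper, or answered aloud to a data collector. No device measure and no blinding are described. Section 5.4.1 sizes both groups alike, "considering 20% lost to follow-up".

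**The concern.** Two separate problems could follow.

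**Retention.** Control families are asked to complete the same series of questionnaires, running to three months after the 12-week period, with no measure aimed at keeping them. If families who stay differ in motivation from those who leave, and the groups lose different proportions, the children compared at T3 and T4 differ in more than the intervention. Section 5.3 mentions a remedial plan for incomplete questionnaires but does not specify it. Section 5.4.2 gives no method for families who are lost.

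**Reporting.** Children aged 6 to 14 in one group may be asked how active they have been around the time when prizes go to those who have progressed. If a child or parent connects the two, reported activity could rise without a change in behaviour, in the direction of the hypothesis in section 5.1.1.

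Allocation is by calendar order, not randomised (section 5.2), so the comparison already has to carry other differences between the groups. An avoidable one should not be added.

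**Working it through.** The plan gives no figure for either effect, so there is none to reproduce. The first two steps compare sections; the last three are illustrations on stated assumptions.

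**1. Who is reached.**

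| Measure | Experimental | Control |
|---|---|---|
| Feedback on the intervention, 4.4(2) | Yes | No intervention to comment on |
| Prizes at group activities and contests, 4.4(3) | Yes | Events not offered |
| Monthly face-to-face interviews, 6.1 | Yes, listed under the programme | Not described |
| Questionnaires, T0 to T4 | Yes | Yes |

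**2. Timing.** Group activities are four-weekly (6.1). T1 and T2 are at the end of weeks 4 and 8, and T3 is at the end of the 12-week programme (sections 6.1 and 7). The rhythm is the same. A shared day is possible, but it is not stated, and no order of questionnaire and prize is set. No prize event is described after week 12, so the reporting question concerns T1 to T3 and not T4.

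**3. Unequal loss and power.** Inputs from 5.4.1: means 35.88 and 166.19, SDs 50.39 and 116.92, 27 per group.
- Difference: 166.19 − 35.88 = 130.31 minutes. The period is not stated.
- Pooled SD: √[(50.39² + 116.92²)/2] = 90.03.
- Power ≈ Φ{130.31 / [90.03 × √(1/nE + 1/nC)] − 1.96}, two-sided 0.05.
- Loss of 20% in each group: 27 × 0.80 = 21.6 each; power 99.7%.
- Assumed loss of 10% v 30%: 24.3 v 18.9; power 99.7%.
- Assumed loss of 5% v 40%: 25.65 v 16.2; power 99.5%.

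Unequal loss on this scale does not endanger power at the planned effect.

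**4. Unequal loss and bias.** Let D be the mean activity of those who stay minus that of those who leave. A group that loses a proportion p has its observed mean shifted by p × D. If D is the same in both groups, the group difference shifts by (pE − pC) × D. Under 10% v 30% this is (0.10 − 0.30) × D = −0.20 × D. With equal loss and equal D it cancels. The documents give no value of D. If D is positive and common to both groups, heavier control loss would shrink the apparent effect. If D differs between groups, the shift can go either way.

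**5. Over-reporting.** Assume no true effect, 21 analysed per group, a constant over-report b in the experimental group, and a simple two-sided z-test at one visit. This test is an illustration, not the repeated-measures analysis in 5.4.2. The standard error is SD × √(2/21).

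| b (minutes) | b / 130.31 | False-positive rate, SD 90.03 | False-positive rate, SD 50.39 |
|---|---|---|---|
| 0 | 0% | 5% | 5% |
| 10 | 7.7% | 6.5% | 9.9% |
| 20 | 15.3% | 11.1% | 25.1% |
| 40 | 30.7% | 30.2% | 73.0% |

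The values of b are assumptions; the documents give no basis for choosing among them.

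**The case against.** The strongest objection concerns reporting. A reader might infer from the prize rule that experimental families are paid to report more activity on the primary outcome. The documents do not say so. The rule opens by confining prizes to staff-run events: "In the offline group parent-child activities and knowledge competitions, reward families, children and parents with outstanding performance and obvious progress". No section links a prize to CLASS-C answers or reported minutes. The weekly self-kept activity record in section 6.2 is an adherence log, not the outcome measure, and nothing says that prizes are based on it. This part of the objection stands. What is left is a possibility: progress is undefined, the outcome is self-reported, and nothing keeps the two apart.

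Prizes can also be read as part of the package, since family competition belongs to the programme and the comparison is with routine care. Section 6.1 does not list them, but the reading is fair, and it is a reason not to ask for the prizes to be removed or narrowed. It does not answer the concern, because inflated reporting is not an effect on activity.

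On retention, a reader might infer that loss will be heavier among controls, or that the trial will lose power. Neither follows. The experimental group carries a target of three 30-minute sessions a week, which could raise its own loss. Several removal reasons in section 4.3 (recurrence, transplantation, death, transfer) have no evident link to prizes. Questionnaires in both groups are checked on the spot and help with completion is offered, which limits missing items at attended visits. These points leave the risk uncertain in size and direction, but they do not supply a retention measure for controls.

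Finally, sequential allocation and an apparently unblinded questionnaire are larger sources of bias than toys and candy. That is true, and it limits the weight of this point.

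**Conclusion.** The point holds as a risk created by one-sided measures. The text establishes that both retention measures reach only the experimental group and that none is described for controls, who are also assessed from T0 to T4. A risk of unequal, motivation-related loss follows. It is a matter of selection bias and not of power, provided the planned effect and pooled SD in 5.4.1 are roughly right.

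Encouragement to over-report is a plausible inference limited to T1 to T3. It rests on the self-reported outcome, the undefined progress criterion and the shared four-weekly rhythm, not on any stated link between prizes and answers. The size of both effects is unknown; the loss rates and over-reporting values above only show what different sizes would do. This is a cheap improvement, not a flaw that invalidates the design.

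**What to change.** Change section 4.4 in three ways:

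1. Give both groups the same small token for returning the questionnaires at each of T1 to T4, whatever activity is reported.
2. Where a group activity falls on an assessment day, collect CLASS-C and the scales before the activity and any prizes.
3. State that prizes are never based on questionnaire answers or on self-recorded activity.

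The prizes themselves can stay in the programme. The cost is protocol wording, a fixed order at existing visits, and low-cost tokens for at least 27 families per group: at most 2 × 27 × 4 = 216 tokens if 27 are enrolled per group and every questionnaire is returned. No sample-size figure changes.
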